Accrual Objective	Kidney transplant recipients (n=5) will receive standard of care (SOC) therapy consisting of alemtuzumab and steroid induction with mycophenolic acid and tacrolimus maintenance immunosuppression, plus induction and treatment for 6 months with belimumab.

Study Design	
This is an open-label pilot-study to evaluate the safety and efficacy of belimumab plus standard of care in the prevention of de novo donor specific antibody in adult subjects after kidney transplantation.
 
We will enroll 5 adult, living donor kidney transplant recipients who are sensitized, evidenced by: Positive sum Donor Specific Antibody (DSA) <1000 MFI and/or Panel of Reactive Antibodies (PRA)>0%. The primary endpoint of this study is de novo DSA production. There are two main reasons for selecting this patient population for our proposed study. 1) Sensitized patients are known to have higher rates of de novo DSA production and 2) Patients with low levels of DSA (sum DSA<1000 MFI) will enable more fidelity in determining the DSA that is produced de novo.

Study Duration:	
Kidney transplant recipients will receive the standard of care (alemtuzumab and steroid induction with mycophenolic acid and tacrolimus maintenance immunosuppression), plus six months of therapy with belimumab. Belimumab 10 mg/kg will be administered IV for 6 months at the following intervals: Day of transplant (Day 0), and then at Weeks 2, 4, 8, 12, 16, and 20 post-transplant.
 
Subjects will be treated for 6 months with belimumab and followed for DSA production for 1 year post transplant.

Primary Study Objectives	
In this proposal we plan to determine (a) whether the addition of belimumab to the standard of care (SOC: alemtuzumab and steroid induction with mycophenolic acid and tacrolimus maintenance immunosuppression) is safe and effective in preventing de novo DSA production at 1, 3, 6, 9, and 12 months post-transplant.
 
Secondary efficacy endpoints will be 1) graft survival and function as determined by serum creatinine/eGFR and urine protein at 1, 3, 6, 9, and 12 months 2) rates of acute cellular and antibody mediated rejection, at 1, 3, 6, 9, and 12 months.

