1.2 Dose Rationale

In this study, belimumab will be administered as 10 mg/kg IV infusions dosed at the same frequency as in the current labeling for SLE.

The selection of belimumab dose was based on review of pooled analyses of safety, efficacy and pharmacokinetic (PK) data from Phase 3 SLE studies. In those studies,

not only for the primary endpoint, but also for some disease activity and flare indices, and for certain critical biomarkers (anti-double-stranded deoxyribonucleic acid (dsDNA) antibodies, complement levels and B-cell subsets), a dose response relationship was seen, with greater differences from placebo for the belimumab 10 mg/kg group than the belimumab 1 mg/kg group. The differences were more marked when only data from subjects with low complement and anti-dsDNA at baseline were analyzed ¹⁴.

In transplantation, unlike SLE or other autoimmune diseases, the event (reperfusion of the allograft) that triggers the pathogenic process is easily identified. In this study, to maximize BLyS binding at the time of this triggering event, the first dose of investigational product will be administered on the day of transplantation intraoperatively. Where possible, study drug infusion should be completed before reperfusion of the allograft.

This study will focus on examining the impact of belimumab during the first 6 months after transplantation, when episodes of rejection are most likely to occur; investigational product will be administered at Day 0, Week 2, Week 4 and then every 4 weeks through Week 20. Subjects will then be observed through the 1-year study period with no further belimumab dosing.

For detailed information of the safety and efficacy of belimumab at each of the doses studied, refer to the IB GlaxoSmithKline Document Number 2011N128591_01 (Investigator's Brochure: Belimumab. Version 11: 20-JUN-2013: always refer to the most recent version).

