3.6 Criteria for Terminating the Study

The Principal Investigator will review safety and efficacy criteria on an ongoing basis. The study enrollment will be halted and data reviewed by the Data Safety Monitoring Committee and the University of Wisconsin Health Sciences Institutional Review Board for any of the following:

- 1) If greater than two patients are discontinued from study treatment due to elevated liver function tests as described in the protocol.
- 2) If greater than two patients develop hypogammaglobulinemia and infectious complications resulting in discontinuation of study treatment
- 3) Death of one or more patients.

After this review, the Investigator, Data Safety Monitoring Committee and the IRB will jointly make a final determination regarding continuation, modification, or termination of the study. The study can be terminated at any time for any reason by the Principle Investigator or GlaxoSmithKline, Inc. Should this be necessary, the patient should be seen as soon as possible. The investigator may be informed of additional procedures to be followed in order to ensure that adequate consideration is given to the protection of the patient's interests. The investigator will be responsible for informing the DMC, IRB and the FDA of the early termination of the trial.

See Section 7.3 for information on the ICTR Data Monitoring Committee (DMC) for this study.

4. Selection of Subjects

Potential subjects will be identified prior to kidney transplant based on the following inclusion and exclusion criteria.

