5.1.2 Treatment monitoring and dose modifying strategies

The following AEs, laboratory assessment results or changes in concurrent medications require evaluation and discussion with the GSK medical monitor within 24 hours of the investigator becoming aware of the event.

Dose Adjustment and Discontinuation

If a subject experiences a clinically significant AE and this AE continues at the next scheduled dose, or could potentially be exacerbated by the next dose, the investigator may delay the next dose by up to 2 weeks or withhold 1 dose, per physician discretion. As a result, any subsequent study visits will be adjusted. If a similar concern is present at the time of the next scheduled dose, any decision made to discontinue treatment will be driven by the Investigator's clinical judgment. Laboratory tests will be repeated per Investigator's discretion.

If it is determined that investigational product should be discontinued, the subject should be followed at regularly scheduled monthly study visits as required until resolution of the AE, and return for follow-up visits as described in Subject Withdrawal Criteria.

For a full listing of the discontinuation criteria, please see section 3.5 of the protocol.

Hypogammaglobulinemia

Benlysta should be discontinued in subjects with IgG levels <250 mg/dL associated with a severe or serious infection. For IgG concentrations < 250 mg/dL that are not associated with a severe or serious infection, increased vigilance for infection is required. Clinical judgment should be applied with respect to the appropriateness of continuing study therapy in these subjects. If a subject experiences any IgG levels < 250 mg/dL, the dose of study agent must be withheld and the Medical Monitor and GlaxoSmithKlein must be consulted before administering any subsequent dose of study agent. If a subject experiences a clinically significant, potentially life-threatening (Grade 4) AE that the investigator believes may be definitely, possibly or probably related to study agent, then treatment with study agent will be discontinued. The subject should be withdrawn from study agent, and followed at regularly scheduled study visits as specified by protocol and also until resolution of the AE(s) (whichever is longer).

Liver Chemistry Stopping Criteria

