6.3.1 Study Treatment

- Belimumab: 10 mg/kg/dose will be administered IV for 6 months at the following intervals: at time of transplant (Day 0), then post -transplant at Weeks 2, 4, 8, 12, 16, and 20.

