7.3 **ICTR Data Monitoring Committee (DMC)**

We plan to utilize the UW ICTR Data Monitoring Committee (DMC) to oversee the study. The UW ICTR DMC is comprised of experienced members (core plus ad hoc) with expertise required to oversee this study. The DMC members will review protocol-specific reports created by statisticians using data pulled from the ICTR OnCore clinical research management system and Research Electronic Data Capture (REDCap) data management tool. These standard reports will include an overview of study objectives, a review of actual and projected accrual rates, an evaluation of patient demographics for balance of randomization, and a summary of the number and seriousness of adverse events. An interim analysis of study results may be performed and source documents may be reviewed to allow the DMC to independently judge whether the overall integrity and conduct of the protocol remain acceptable based on data provided and reported by the Principal Investigator. The DMC will make recommendations to the Principal Investigator that could include actions of continuation, modification, suspension, or termination.

In providing oversight for the conduct of this study, the ICTR DMC will meet biannually during the study to review all adverse events. Additional meetings may be scheduled as determined by the DMC or as requested by the PI. The predefined stopping points for this study are described in section 3.6 of this protocol. We will submit all reportable events to the DMC and the Health Sciences IRB in accordance with their reporting guidelines.

8. Ethical Considerations and Compliance in Good Clinical Practice

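### Halt criteria 1 and 2 count only toxicity that ends belimumab dosing, so after a subject's Week 20 dose they can count nothing for the remaining 32 of 52 weeks

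*Combined protocol and SAP*

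**What the plan says.** The study enrols five subjects in a single arm (synopsis: "Kidney transplant recipients (n=5) will receive standard of care (SOC) therapy"). Section 3.6 lists three conditions under which enrolment is halted and the data are reviewed:

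- Criterion 1: "If greater than two patients are discontinued from study treatment due to elevated liver function tests as described in the protocol".
- Criterion 2: "If greater than two patients develop hypogammaglobulinemia and infectious complications resulting in discontinuation of study treatment".
- Criterion 3: "Death of one or more patients".

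After the review, the investigator, the monitoring committee and the IRB decide jointly whether the study goes on, is changed or ends. Section 7.3 gives these conditions formal standing: "The predefined stopping points for this study are described in section 3.6 of this protocol".

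Section 6.3.1, headed Study Treatment, lists only belimumab, given "at time of transplant (Day 0), then post -transplant at Weeks 2, 4, 8, 12, 16, and 20". Section 1.2 adds: "Subjects will then be observed through the 1-year study period with no further belimumab dosing".

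Section 5.1.2 treats interruption as a step short of discontinuation. For a clinically significant adverse event, "the investigator may delay the next dose by up to 2 weeks or withhold 1 dose, per physician discretion". It calls for discontinuation when IgG is below 250 mg/dL with a severe or serious infection, and when a listed liver chemistry criterion is met. For IgG below 250 mg/dL without such an infection, the dose is withheld pending consultation, and whether to continue is left to judgment.

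Appendix A schedules the immunoglobulin panel and the comprehensive metabolic panel through Month 12.

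**The concern.** Criteria 1 and 2 require that treatment be stopped because of the toxicity. While a subject is being dosed, this is a workable marker of severity. Once dosing is complete the marker no longer exists: the same liver event or the same low IgG with infection produces no discontinuation, and so no count.

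The rule is the study's only numeric safety trigger apart from death. Section 1.3 says there is no experience of belimumab combined with alemtuzumab or tacrolimus, and names infection among the risks to be mitigated. If events in earlier subjects after Week 20 do not count, the joint review may not be called while later subjects are still being enrolled or dosed, even though the data that would show the events are being collected.

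**Working it through.** The plan gives no operating characteristics for the halt rule, so there is no stated figure to reproduce. The main check is of the text; the probabilities are illustration only.

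**1. Threshold.** More than two of five means at least 3 of 5 (60%).

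**2. Uncounted time per subject.** Last scheduled dose Week 20; one year taken as 52 weeks. 52 − 20 = 32 weeks; 32/52 = 62%. If Month 12 is read as Week 48, (48 − 20)/48 = 28/48 = 58%. A permitted dose delay can move the last dose somewhat later.

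**3. Two cases side by side.** Three subjects each have IgG below 250 mg/dL with a serious infection.

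- All three events occur during dosing and section 5.1.2 is followed: three discontinuations, count 3, halt and review.
- Two occur during dosing and one at Week 24: two discontinuations, count 2, no halt.

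The toxicity is the same in both cases; only its timing relative to the last dose differs.

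**4. Illustrative size.** Assumptions not in the documents: independent subjects, constant hazard over 52 weeks, one toxicity type, and every event during dosing ending in discontinuation. With true 12-month risk p, the risk that can be counted as written is q = 1 − (1 − p)^(20/52). The table gives the binomial probability of at least 3 of 5.

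| p | q | As written (to Week 20) | Counted to Month 12 |
|---|---|---|---|
| 0.1 | 0.040 | 0.06% | 0.9% |
| 0.2 | 0.082 | 0.5% | 5.8% |
| 0.3 | 0.128 | 1.7% | 16.3% |
| 0.4 | 0.178 | 4.3% | 31.7% |
| 0.5 | 0.234 | 8.7% | 50.0% |

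On a 48-week basis, the as-written values at p = 0.3 and 0.5 are 2.1% and 10.4%.

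**5. Can a late event still matter?** Accrual is not stated, so assume even spacing of k months. Week 20 is 20 × 12/52 = 4.6 months.

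- *Fifth enrolment, all three events late in subjects 1 to 3.* The third subject enrols at 2k and passes Week 20 at 2k + 4.6; the fifth enrols at 4k. The halt comes in time only if 4k > 2k + 4.6, so k > 2.3 months. That is the best case. If the third subject's event falls mid-window, at Week 36 (36 × 12/52 = 8.3 months), then 4k > 2k + 8.3 and k > about 4.1 months.
- *Fifth subject still being dosed.* Dosing of the fifth subject ends at 4k + 4.6. A third-subject event x months after that subject's own Week 20 falls at 2k + 4.6 + x. It precedes the fifth subject's last dose when x < 2k. With any staggered accrual there is therefore a period in which a late event could inform a subject under treatment.

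**The case against.** The strongest reply is that oversight does not stop at Week 20. Under section 3.6 the investigator reviews safety continuously, and the investigator or the funder may end the study at any time. Under section 7.3 the committee reviews all adverse events twice a year, can hold extra meetings, and can recommend suspension or termination. Serious events are reported under sections 7 and 7.2.1. All of this stands. A reader might infer that late toxicity cannot reach a review at all; the documents do not support that. What is missing is an automatic count.

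A reader might also infer that the criteria ignore toxicity during dosing, or that withheld doses leave a large gap. That is too strong. The discontinuation must result from the named toxicity, and section 5.1.2 already calls for discontinuation at the listed liver thresholds and for IgG below 250 mg/dL with a severe or serious infection. A subject whose dose is first withheld and who is later discontinued for the listed reason does count. The one open question is whether a withheld final dose, with none to follow, is a discontinuation.

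Two supporting arguments should not be used. Only the 6-month valganciclovir course in section 5.1.1 ends after Week 20; the 3-month acyclovir course ends before it. The documents also give no IgG time course, so they cannot show that the immunoglobulin effect of the full course emerges only after the last dose.

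Finally, it can be said that a five-subject descriptive pilot may reasonably tie its rule to exposure, since late infections are hard to attribute given the background immunosuppression. That limits the weight of the point, but does not explain why an equally severe event should drop out of the count at Week 20.

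**Conclusion.** The point holds as a gap in the counting rule. For each subject who completes dosing, criteria 1 and 2 cannot count an event in the last 32 of 52 weeks (62%; 58% if Month 12 is Week 48), and death is the only automatic trigger left. This takes study treatment to mean belimumab, as section 6.3.1 does; section 3.6 does not define the term. Section 7 also describes safety monitoring for 12 months from discontinuation of treatment, which would lengthen the uncounted period.

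The gap is per subject: others still being dosed can count. The effect on enrolment depends on accrual, which is not stated, and once all five are enrolled only the review has effect. That review can still change or end treatment for subjects being dosed. The probabilities show direction under assumed rates and are not estimates for this trial. The change is worth making because it is cheap and uses data already scheduled.

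**What to change.** In section 3.6, keep the present counts of discontinuations and the present threshold. Add to each criterion any subject who, after the last belimumab dose and through Month 12, has an event of the type named in that criterion which, under section 5.1.2, would have called for discontinuation had dosing been ongoing.

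- **Add, do not replace.** Criterion 2 sets no IgG cut-off and no infection severity. A milder case that leads to discontinuation counts today and would be lost if the section 5.1.2 threshold replaced the present wording.
- **Withheld final dose.** State whether a last scheduled dose withheld for such an event counts as a discontinuation.
- **Reconcile section 5.1.2.** The liver stopping list includes ALT at or above 5 times the upper limit of normal. The later text on increased monitoring lets subjects with ALT from 5 to below 8 times that limit continue with weekly monitoring if bilirubin is below twice the limit and there are no symptoms. The sponsor must reconcile these passages, because they decide who counts under criterion 1.
- **Liver items tied to monitoring.** Some items turn on whether weekly monitoring is possible. State which apply once dosing has ended.

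No dosing or stopping rule for an individual subject changes, and no new data, staff or committee is needed. The cost is one added clause per criterion plus these clarifications, and a somewhat higher chance of a review pause, including for late infections that are hard to attribute to belimumab.

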4.1 Inclusion Criteria

- Male or female subjects 18-60 years of age
- Planned to receive a living donor kidney transplant
- Sensitized patients: Positive sum DSA <1000, and/or PRA>0%.
- Subjects must be capable of understanding the purpose and risks of the study and must sign a statement of informed consent.
- Female subjects must be post-menopausal, surgically sterilized, or she and/or sexual partner must be willing to use an acceptable method of birth control with a <1% failure rate as stated in the product label from time of study consent, during study participation, and for 16 weeks after the last dose of the study agent (i.e., contraceptive subdermal implant of levonorgestrel or etonogestrel, intrauterine device or intrauterine system, combined estrogen and progestogen oral contraceptive, Injectable progestogen, contraceptive vaginal ring, percutaneous contraceptive patches, or abstinence) for the duration of the study. Male partner sterilization with documentation of azoospermia prior to the female subject's entry into the study, and this male is the sole partner for that subject. The documentation of male sterility can come from the site personnel's: review of subject's medical records, medical examination and/or semen analysis, or medical history interview provided by her or her partner. Note: Mycophenolate mofetil (MMF) affects the metabolism of oral contraceptives and may reduce their effectiveness. As such, women receiving MMF who are using oral contraceptives for birth control should employ an additional method (e.g., barrier method). Mycophenolate can cause fetal harm when administered to a pregnant female. Use of mycophenolate during pregnancy is associated with an increased risk of first trimester pregnancy loss and an increased risk of congenital malformations. Mycophenolate affects the metabolism of oral contraceptives and may reduce their effectiveness. As such, women receiving MMF who are using oral contraceptives for birth control should employ an additional method (e.g., barrier method) resulting in two reliable forms of contraception being used simultaneously before starting study treatments, during therapy, and for 6 weeks after stopping therapy; unless abstinence is the chosen method of contraception
- Female patients of childbearing potential must have a negative serum pregnancy test within 48 hours of transplant. Must be willing to use contraceptives from the time of study consent, during study participation, and for 16 weeks after the last dose of study agent. For sexually active men, condoms should be used during, and for at least 90 days after cessation of mycophenolate treatment. No sperm donation should be made during this period of time. For female partners of male subjects, it is recommended to use highly effective contraception during treatment and for 90 days after the last dose of mycophenolate
- No blood donation should be made by the study subjects during mycophenolate treatment and for at least 6 weeks after stopping mycophenolate treatment
- If stricter female or male contraception requirements are specified in the countryspecific label for any study related therapies, they must be followed.
- Male subjects must agree to use an acceptable method for contraception for the duration of the study.

Female patients of childbearing potential must have a negative serum pregnancy test within 48 hours of transplant. Must be willing to use contraceptives from the time of study consent, during study participation, and for 16 weeks after the last dose of study agent. Reproductive Status: Definition of Women of Child-Bearing Potential (WOCBP). WOCBP comprises women who have experienced menarche and who have not undergone successful surgical sterilization (hysterectomy, bilateral tubal ligation, or bilateral oophorectomy) or who are not post-menopausal (see definition below).

Post-menopause is defined as:

- Women who have had amenorrhea for \square 12 consecutive months (without another cause) and who have a documented serum follicle-stimulating hormone (FSH) level > 35 mIU/mL.
- Women who have irregular menstrual periods and a documented serum FSH level > 35 mIU/mL.
- Women who are taking hormone replacement therapy (HRT).

The following women are WOCBP:

- Women using the following methods to prevent pregnancy: Oral contraceptives, other hormonal contraceptives (vaginal products, skin patches, or implanted or injectable products), or mechanical products such as intrauterine devices or barrier methods (diaphragm, condoms, spermicides).
- Women who are practicing abstinence from intercourse from 2 weeks prior to administration of the 1st dose of study agent until 16 weeks after the last dose of study agent (Sexual inactivity by abstinence must be consistent with the preferred and usual lifestyle of the subject. Periodic abstinence (e.g. calendar, ovulation, symptothermal, post-ovulation methods) and withdrawal are not acceptable methods of contraception) \square Women who have a partner who is sterile (e.g., due to vasectomy).

WOCBP must be using an acceptable method of contraception to avoid pregnancy from the time of consent with $<1\%$ failure rate as stated in the product label throughout study participation, and for 16 weeks after the last dose of study drug in such a manner that the risk of pregnancy is minimized. Acceptable methods of contraception include: complete abstinence, any form of intra-uterine devices (without hormones), tubal sterilization or your partner has had a vasectomy.

Other acceptable forms of birth control include choosing one hormonal and one barrier method or double-barrier methods. Barrier methods include Essure®, male or female condom, diaphragm with spermicide, shield, cap with spermicide, contraceptive sponge, and spermicidals. Hormonal methods include oral contraceptive pills, transdermal patches, vaginal rings, progesterone-only, and injections. Periodic abstinence (for example, calendar, ovulation, symptothermal, post-ovulation methods) and withdrawal are not acceptable methods of contraception.

- These allowed methods of contraception are only effective when used consistently, correctly and in accordance with the product label. The investigator is responsible for ensuring subjects understand how to properly use these methods of contraception.

- WOCBP must have a negative serum pregnancy test result (minimum sensitivity 25 IU/L or equivalent units of HCG) within 48 hours prior to transplant (and the first dose of study drug intraoperatively). Women must not be breast-feeding

4.2 *Exclusion Criteria*

- ABO incompatible donor kidney
- Deceased donor
- KDPI \geq 85%
- HLA identical or matched kidney
- Transplant other than kidney: has previously received a hematopoietic stem cell/marrow transplant or an organ transplant other than a kidney (with the exception of corneal transplantation)
- T- and/or B-cell positive crossmatch by complement dependent cytotoxicity or flow cytometry against the recipient
- Currently on any suppressive therapy for a chronic infection (such as tuberculosis, pneumocystis, cytomegalovirus, herpes simplex virus, herpes zoster and atypical mycobacteria).
- Hospitalization for treatment of infection within 60 days of Day 0
- Use of parenteral (IV or IM) antibiotics (antibacterials, antivirals, anti-fungals, or anti parasitic agents) within 60 days of Day 0
- Have a history of a primary immunodeficiency
- Uncontrolled infection or any other unstable medical condition that could interfere with the study
- Seropositive for HIV, HCV or HBV, except for hepatitis B surface antibody positive If the HIV, HCV or HBV screening virology results are not available prior to transplantation then the most recent historical result (within the last 6 months) will be used.
- Have a significant IgG deficiency (IgG level < 400 mg/dl) Have an IgA deficiency (IgA level < 10 mg/dL)
- Prior therapy at any time: has ever received any of the following: a) B-cell targeted therapy (e.g., rituximab, other anti-CD20 agents, anti-CD2 [epratuzumab], antiCD52 [alemtuzumab], BLyS-receptor fusion protein [BR3], TACI fragment, crystallizable (Fc), belimumab), or IV cyclophosphamide
- Live vaccines within 30 days
- Have a history of an anaphylactic reaction to parenteral administration of contrast agents, human or murine proteins or monoclonal antibodies
- Patients with a lymphocyte count <500/mm³
- Patients with evidence of current drug or alcohol abuse or dependence.
- Patients with venous access limitations likely to preclude monthly infusions
- Patients whom are unlikely to comply with scheduled study visits based on investigator judgment or has a history of substance abuse, psychiatric disorder or condition that may compromise communication with the investigator
- Myocardial infarction within 6 months prior to enrollment or New York Heart Association (NYHA) Class III or IV heart failure, uncontrolled angina, severe uncontrolled ventricular arrhythmias, or electrocardiography evidence of acute ischemia or active conduction system abnormalities
- Diagnosis of liver cirrhosis or chronic viral hepatitis

- Female subject is pregnant or breast-feeding. Confirmation that the subject is not pregnant must be established by a negative serum β -human chorionic gonadotropin (β -hCG) pregnancy test result obtained during screening. Pregnancy testing is not required for post-menopausal or surgically sterilized women
- Patient has received other investigational drugs within 365 days before enrollment
- Serious medical or psychiatric illness likely to interfere with participation in this clinical study
- Have evidence of serious suicide risk including any history of suicidal behavior in the last 6 months and/or any suicidal ideation in the last 2 months or who in the investigator's judgment, pose a significant suicide risk
- Diagnosed or treated for malignancy within 5 years of enrollment, with the exception of complete resection of basal cell carcinoma or squamous cell carcinoma of the skin, an in situ malignancy, or low-risk prostate cancer after curative therapy.
- Have any other clinically significant abnormal laboratory value in the opinion of the investigator

5. Treatment

5.1 *Immunosuppression Protocol*

The immunosuppressive therapy will consist of the standard of care (SOC) alemtuzumab and steroid induction with mycophenolic acid and tacrolimus maintenance immunosuppression and belimumab 10 mg/kg IV administered for 6 months at the following intervals: at time of transplant (Day 0), then post-transplant at 2, 4, 8, 12, 16, and 20 weeks.

5.1.1 *Antibacterial, antiviral, and antifungal prophylaxis*

Antibacterial, antiviral for CMV prophylaxis, and antifungal prophylaxis therapy will be administered and adjusted per institutional standard of care. Recommended prophylaxis per current institutional standard of care includes:

- Antibacterial prophylaxis: Sulfa-Trimethoprim Double Strength (Bactrim DS) 800-160 MG per tablet daily for one year
- Antiviral CMV prophylaxis per donor/recipient CMV risk profile:
 - High or moderate CMV risk: Donor seropositive/Recipient seronegative [D+/R-], Donor seropositive/Recipient seropositive [D+/R+], or Donor seronegative/Recipient seropositive [D-/R+]:
 - Valganciclovir 900 mg orally daily for 6 months. Dosing adjusted for renal function.
 - Low CMV risk: Donor seronegative/Recipient seronegative [D-/R-]:
 - Acyclovir 400 mg twice daily orally for 3 months. Dosing adjusted for renal function.
- Antifungal prophylaxis:
 - Nystatin 5 mL swish and swallow for one month

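### The post-menopause definition takes in women who still have periods and any woman on HRT, lifts the pregnancy-test and contraception requirements for them, and conflicts with the WOCBP wording

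*Combined protocol and SAP*

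**What the plan says.** Section 4.1 lists three routes to post-menopause, and the synopsis repeats them:

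- Route 1: amenorrhea for at least 12 "consecutive months (without another cause) and who have a documented serum follicle-stimulating hormone (FSH) level > 35 mIU/mL".
- Route 2: "Women who have irregular menstrual periods and a documented serum FSH level" above 35 mIU/mL.
- Route 3: "Women who are taking hormone replacement therapy (HRT", with nothing further attached.

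Several requirements depend on this status.

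- **Contraception.** Section 4.1 treats it as an alternative to birth control: "Female subjects must be post-menopausal, surgically sterilized, or she and/or sexual partner must be willing to use an acceptable method of birth control".
- **Screening test.** The pregnancy exclusion in Section 4.2, and its counterpart in the synopsis, states: "Pregnancy testing is not required for post-menopausal or surgically sterilized women".
- **Later tests.** Section 7 and footnote 8 of Appendix A require tests before transplant and before each belimumab dose, but only for WOCBP.
- **WOCBP.** Section 4.1 describes these as women past menarche who have not been surgically sterilized, "or who are not post-menopausal (see definition below". A list follows that counts as WOCBP women who use contraceptives, practise abstinence or have a sterile partner.

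On the hazard, Section 4.1 says: "Mycophenolate can cause fetal harm when administered to a pregnant female". Section 7 repeats the warning. Section 4.1 also asks for contraception until 16 weeks after the last dose of study agent.

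**The concern.** Route 1 requires a full year without periods, no other explanation for it, and a raised FSH. Route 2 describes a woman who still has periods and asks only for one documented FSH value. Route 3 asks for neither, in a trial open to ages 18 to 60. A woman who could not qualify by route 1 can therefore gain the same status, and the same waivers, by route 2 or 3.

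What is at stake is participant safety and the working of the protocol's own pregnancy exclusion. A site that follows the text as written could enrol a woman who may be fertile, without a required pregnancy test or contraception, and start a drug that the protocol says can harm a fetus. The Section 3.5 instruction to contact staff at once if pregnancy is suspected is also addressed to WOCBP, so that backstop would not be aimed at her.

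**Working it through.** No sample size, power or event figure is involved. The check traces the definition through the text and counts the tests affected.

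**Step 1: classify unsterilized women by each rule.**

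| Woman | Post-menopause routes | WOCBP sentence, read literally | WOCBP list | Waivers in 4.1 and 4.2 |
|---|---|---|---|---|
| A. Irregular periods, one FSH above 35 on record, no contraception, abstinence or sterile partner | Post-menopausal (route 2) | WOCBP | Not listed | Apply |
| B. On HRT, no contraception, abstinence or sterile partner | Post-menopausal (route 3) | WOCBP | Not listed | Apply |
| C. On HRT, and uses contraception or is abstinent | Post-menopausal (route 3) | WOCBP | Listed | Apply by status; contradicted by the list |
| D. Twelve months without periods, FSH above 35, no contraception, abstinence or sterile partner | Post-menopausal (route 1) | WOCBP | Not listed | Apply |

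**Step 2: the WOCBP sentence.** It joins its two conditions with *or*: not sterilized, or not post-menopausal. Every woman in the table is unsterilized, so the first condition is met and all four are WOCBP. That would require testing and contraception, against the waivers. If the sentence was meant to read *and*, A, B and D are not WOCBP and the waivers are consistent with it, but then A and B have no required safeguard. One reading gives a contradiction, the other a gap.

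**Step 3: overlap.** Woman C is post-menopausal by route 3 and WOCBP by the list. No rule says which prevails.

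**Step 4: tests affected.** Appendix A marks serum pregnancy tests as follows:

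- Screening and Day 0: 2, both marked as standard of care.
- Before the doses at Weeks 2, 4, 8, 12, 16 and 20: 6, all marked as research procedures.
- Maximum: 2 + 6 = 8.
- Day 0 may fall on the same day as screening, so one test could serve both: 8 − 1 = 7.

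**Step 5: possible safeguards elsewhere.** Section 4.1 makes any stricter country-specific label rule on contraception binding. This could restore a contraception requirement for A and B, but it changes neither the definition nor the test waiver, and the documents quote no label text. The WOCBP list does not reach A or B, who by construction fit none of its entries.

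**The case against.** The strongest points on the other side are these.

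- **The routes are alternatives.** A reader might infer that the three bullets contradict one another. They do not: alternatives of differing strictness can coexist. This stands. The problem is what routes 2 and 3 allow, together with the conflict with the WOCBP wording.
- **Fertility is not quantified.** The documents give no pregnancy risk for women with irregular periods and a raised FSH, or for HRT users. This stands, and that such a woman may conceive is an assumption. It has some support in the protocol, where route 1 does not accept a raised FSH without a year of amenorrhea.
- **Not required is not the same as not done.** Nothing forbids testing or counselling, pregnancy remains an exclusion, and two of the tests are standard of care that a clinic may run regardless. This stands and limits the size of the point.
- **The literal WOCBP sentence protects these women.** It would, but only by contradicting the explicit waivers. A site cannot rely on it.
- **The stricter-label clause and the WOCBP list narrow the group.** They do, but neither reaches the pregnancy-test waiver for a woman who uses no contraception.
- **FSH is absent from the screening list and Appendix A.** A reader might call this an omission. The text asks for a documented value, so an existing record suffices and no schedule entry is needed.

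**Conclusion.** The point holds as a safety and consistency matter. By the text, irregular periods with one documented FSH above 35 mIU/mL, or HRT use alone, confers post-menopausal status. That status removes the requirement for up to 8 scheduled pregnancy tests and for contraception under the protocol, unless a stricter label applies. Separately, the literal WOCBP sentence and the WOCBP list conflict with the waivers.

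The conclusion rests on two assumptions: that some women admitted by routes 2 and 3 can still conceive, and that sites would act on the waivers rather than on the literal WOCBP sentence.

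Two stronger inferences are not supported. One is that such a woman would certainly miss every test: 8 is a maximum, and a waived requirement does not mean an untested patient. The other is that a stated share of the sample is exposed. One woman would be 1/5 = 20% of the planned 5 subjects, but the documents give no expected number and it may be zero. The endpoints and the descriptive analysis in Section 9 are not affected.

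**What to change.** The sponsor and its clinical experts should reconcile the following into one consistent definition:

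- the post-menopause bullets, the WOCBP sentence and the WOCBP list in the synopsis and Section 4.1;
- the contraception alternative in Section 4.1 and its synopsis counterpart;
- the pregnancy-test waiver in Section 4.2 and its synopsis counterpart;
- the limits to WOCBP in Section 7 and Appendix A footnote 8.

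The result should give each woman one unambiguous status, say which heading prevails when two apply, and make the testing and contraception waivers fit the protocol's own fetal-harm warning. Which definition to adopt is for the sponsor; none is proposed here.

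The cost is small: rewording the definition in two places, checking that the dependent sections agree with it, and possibly a few more hCG tests at visits where blood is already drawn. Sample size, endpoints and analysis stay as they are.
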